11.2.2 Handling of subjects after definitive treatment discontinuation

Subjects will be followed up, unless he/she withdraws consent for follow-up, according to the study procedures as specified in this protocol up to the scheduled date of study completion (ie, 5 years after the initial treatment), or up to recovery or stabilization of a followed-up adverse event, whichever comes last.

As far as possible, after the permanent discontinuation of Sculptra® Aesthetic treatment, all examinations scheduled for the final study day must be performed on all subjects who receive the Sculptra® Aesthetic but do not complete the study according to clinical trial protocol.

For all definitive treatment discontinuations, when considered as confirmed, the reason for and date of withdrawal must be recorded by the Investigator in the appropriate pages of the CRF and in the subject's medical records.

11.3 PROCEDURE FOR WITHDRAWAL OF SUBJECTS FROM STUDY FOLLOW-UP SCHEDULE

The subjects may withdraw from the study follow-up schedule, before study completion if they decide to do so, at any time and irrespective of the reason, or this may be the Investigator's decision (eg, noncompliance with clinical trial protocol requirements):

- All study withdrawals should be recorded by the Investigator in the appropriate CRF pages when considered as confirmed.
- If possible, the subjects are assessed using the procedure normally planned for the end-of-study.

In the event that a subject is lost to follow-up, the Investigator should make every effort to contact the subject, to identify the reason why he/she failed to attend the visit, and to determine his/her health status, including at least his/her vital status. Attempts to contact such a subject using the information provided by the subject during the study, will include 3 attempts to contact the subject's telephone number(s) of record, followed by 2 certified letters to the mailing address provided by the subject. These must be documented in the subject's records (eg, times and dates of attempted telephone contact, receipt for certified letters that were sent).

The statistical analysis plan will specify how these subjects without primary endpoints will be considered.

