8.8 CONCOMITANT TREATMENT

No concomitant facial injectable dermal fillers (including Sculptra® Aesthetic) will be allowed during the first 2 years after the initial single treatment regimen.

The following medications/fillers and procedures are prohibited in the facial area for the first 2 years of the study, after which they may be used only above the zygoma at the discretion of the Investigator:

• Procedures/treatments

CONFIDENTIAL

- Botulinum toxin products (eg, Botox cosmetic® injections, etc.)
- Nonpermanent cosmetic filler-type products (eg, bovine collagen, hyaluronic acids, etc.).
- Cosmetic permanent filler-type injectable products (eg, PMMA, silicone, preformed implant, etc.).
- Superficial dermal resurfacing procedures including chemical peel, dermabrasion, or microderm treatments.
- Deep dermal resurfacing procedures including laser therapy.
- Prescription facial wrinkle therapies, prescription strength alpha-hydroxyacids and beta-hydroxyacids applied in the treatment area.

The following treatments/medications are prohibited for the entire 5-year duration of the study:

- Any investigational product or device
- Procedures/treatments
 - Sculptra® Aesthetic treatment in any anatomical site
 - Cosmetic permanent and nonpermanent filler-type injectable products in the Sculptra® Aesthetic treated facial area
 - Deep dermal resurfacing procedures including laser therapy in the Sculptra® Aesthetic treated facial area
 - Superficial dermal resurfacing procedures including chemical peel, dermabrasion, or microderm treatments in the Sculptra® Aesthetic treated facial area.

• Medications

- Immunosuppressive medications including systemic steroids (eg, oral prednisone) for more than 1 month over the duration of the study. Intranasal/inhaled and topical steroids are allowed.

• Devices:

- Hand-held light therapy devices for personal use such as light emitting diode (LED) or other in the treatment area.
- Medications at the discretion of the Investigator:
 - Subjects requiring antiplatelet (eg, full strength aspirin [> 81 mg/per day], high-dose aspirin-containing products, clopidogrel, etc.); anticoagulant (eg, coumarin derivatives, unfractionated heparin, low molecular weight heparin, selective factor Xa inhibitor, thrombin inhibitor, etc.) or nonsteroidal anti- inflammatory agents; in whom, in the Investigator's opinion, administration of Sculptra® Aesthetic may cause procedure-related complications at the injection site.

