10.7 PREGNANCY

- Pregnancy will be recorded as an adverse event in all cases. It will be reported following the same procedure as for adverse events related to Sculptra® Aesthetic.
- In the event of pregnancy during the study, Sculptra® Aesthetic should be discontinued and the Sponsor/designee should be informed by contacting the representative of the monitoring team within 24 hours of knowledge.
- In the event of pregnancy, the pregnancy reporting form along with the SAE Reporting Form should be filled out and sent to the representative of the monitoring team within 24 hours of knowledge (see Section 10.3).
- Follow-up of the pregnancy (mother and fetus/child) will be mandatory through delivery or other end of the pregnancy (eg, abortion) and during the 5 year follow-up, whichever is the latest.

11 HANDLING OF SUBJECT TEMPORARY OR DEFINITIVE TREATMENT DISCONTINUATION AND OF SUBJECT STUDY DISCONTINUATION

Sculptra® Aesthetic should be continued whenever possible. In case Sculptra® Aesthetic is stopped, it should be determined if the stop can be made temporarily; permanent Sculptra® Aesthetic discontinuation should be a last resort. Any Sculptra® Aesthetic discontinuation should be fully documented in the CRF. In any case, the subject should remain in the study as long as possible.

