11.2 DEFINITIVE TREATMENT DISCONTINUATION WITH INVESTIGATIONAL PRODUCT

11.2.1 Criteria for definitive treatment discontinuation with investigational product

Subjects must be withdrawn from receiving any further Sculptra® Aesthetic for the following reasons:

- *At their own request*: In case the subject wishes to discontinue treatment the Investigator must inquire and document in the medical record whether:
 - the subject decides to discontinue study treatment but agrees to follow-up procedures required by the clinical trial protocol,
 - the subject decides to discontinue study treatment and all follow-up procedures,
 - the subject decides to revoke the consent to collect and process further data.
- If, in the Investigator's opinion, continuation in the study would be detrimental to the subject's well-being (eg, serious adverse events)
- *Pregnancy:* Pregnancy will lead to definitive discontinuation of any further Sculptra® Aesthetic treatment in all cases.

The Investigator may withdraw the subject from any further Sculptra® Aesthetic treatment due to the following reasons:

- Use of prohibited concomitant medications that will interfere with the analysis of the study
- Use of another investigational drug or device

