11.4 CONSEQUENCE

Subjects who have been withdrawn from the study cannot be reincluded in the study. Their subject number must not be reused. In specific situations to be discussed between Investigator and Sponsor or designee, subjects who have not yet been treated can be reincluded in the study with a new number.

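### Protocol Section 11.3 lets the investigator end 5-year safety follow-up for noncompliance, and a subject removed without an adverse event of interest is then counted as event-free

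*Protocol*

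**What the plan says.** Protocol Section 11.3 governs leaving the follow-up schedule. Subjects may go at any time and for any reason, "or this may be the Investigator's decision (eg, noncompliance with clinical trial protocol requirements". Section 11.4 makes this final for a treated subject: "Subjects who have been withdrawn from the study cannot be reincluded in the study".

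Three neighbouring texts bear on the same decision:

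- The opening paragraph of Section 11 says: "In any case, the subject should remain in the study as long as possible".
- Section 11.2.2, on subjects who have definitively stopped treatment, says: "Subjects will be followed up, unless he/she withdraws consent for follow-up, according to the study procedures as specified in this protocol". Withdrawal of consent is the only exception it states.
- Section 11.2.1 lists "Use of prohibited concomitant medications that will interfere with the analysis of the study" among the reasons for which the investigator may withdraw a subject from further treatment. It does not mention follow-up for that case.

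Section 8.8 supplies the requirement most likely to be breached. It begins: "No concomitant facial injectable dermal fillers (including Sculptra® Aesthetic) will be allowed during the first 2 years". For the full 5 years it also prohibits "Cosmetic permanent and nonpermanent filler-type injectable products in the Sculptra® Aesthetic treated facial area", together with superficial and deep resurfacing there.

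Both co-primary endpoints are incidences over 5 years (Protocol Section 13.3.2.1), and ITT is the primary population for testing (Section 13.4.2). Protocol Section 13.7 and SAP Section 5.2.1 treat a subject who discontinues without an event as having none up to the time point tested.

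**The concern.** The purpose of follow-up here is to see what happens around an implant that is already in place. A subject who breaks a cosmetic restriction in Year 3 can still be examined for nodules, granulomas or pigment change. Section 11.3 allows that observation to stop for a reason that has nothing to do with whether safety can be observed.

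The situation is foreseeable. Participants enrolled to have facial folds corrected, receive one regimen, and are asked to accept no filler or resurfacing in the treated area for the rest of the 5 years. At stake is the completeness of the 5-year incidence. Under the plan's missing-data rule, time not observed becomes time without events.

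**Working it through.** **1. The texts side by side.**

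| Source | Who is covered | What may end | On what ground |
|---|---|---|---|
| Section 11, opening | all subjects | nothing; general wish to retain | none stated |
| Section 11.2.1 | subjects under treatment | further treatment | includes prohibited concomitant medication |
| Section 11.2.2 | after definitive treatment discontinuation | follow-up | withdrawal of consent |
| Section 11.3 | all subjects | follow-up | subject's choice, or investigator's decision, for example noncompliance |

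The direct conflict, Section 11.2.2 against Section 11.3, exists only for subjects who definitively stopped treatment. For a subject who finished the regimen, Section 11.3 is a permissive rule that sits against the retention statement in Section 11 and against the 5-year endpoints.

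**2. The route for a late procedure.** After about Week 9, withdrawal from further treatment under Section 11.2.1 has no practical effect. If a subject has a filler placed in the treated area later, the withdrawal provision that remains is Section 11.3. That leads to no return (Section 11.4) and to the event-free assumption (Protocol Section 13.7, SAP Section 5.2.1). A missed event can only lower the counted incidence.

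**3. The plan's own numbers.** Protocol Section 7.1 gives 863 enrolled for 604 evaluable, 22 for 15 (skin type IV) and 122 for 85 (types V-VI). With N = n/(1 - d) and d = 0.30:

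- 604/0.70 = 862.9, rounded up to 863
- 15/0.70 = 21.4, rounded up to 22
- 85/0.70 = 121.4, rounded up to 122

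All three reproduce. The 30% is inferred, since the text of Section 13.2 is not public. The allowance is 863 - 604 = 259 subjects. The margins are 22 - 15 = 7 (type IV) and 122 - 85 = 37 (types V-VI).

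**4. Effect on evaluable numbers.** Assume a share w of subjects is withdrawn for noncompliance, with w from 2% to 10%. The documents give no source for this range. That is 0.02 × 863 = 17 to 0.10 × 863 = 86 subjects.

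- If these already sit inside the 30%, nothing extra is lost. They use 17/259 = 7% to 86/259 = 33% of the allowance.
- If they come on top, 863 × (0.70 - w) gives 587, 561 and 518 evaluable at 2%, 5% and 10%. Types V-VI would have 122 × (0.70 - w) = 83.0, 79.3 and 73.2 against the 85 committed.

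**5. Effect on observed incidence.** Let p = 20/116 = 17.24% (pivotal nodule/papule rate, Protocol Section 4), RR the relative risk in withdrawn subjects, and f the share of their first events falling after withdrawal. The understatement is w × RR × p × f, in percentage points:

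| w | RR = 1, f = 0.25 to 0.50 | RR = 2, f = 0.25 to 0.50 |
|---|---|---|
| 2% | 0.09 to 0.17 | 0.17 to 0.34 |
| 5% | 0.22 to 0.43 | 0.43 to 0.86 |
| 10% | 0.43 to 0.86 | 0.86 to 1.72 |

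The f range is an assumption and may be high. In the pivotal study, new related events more than 13 months after first injection arose in 3 subjects, so at most 3/20 = 15% of the nodule/papule subjects. With f = 0.15, w = 5% and RR = 1 the understatement is 0.05 × 17.24 × 0.15 = 0.13 points. With w = 10% and RR = 2 it is 0.10 × 2 × 17.24 × 0.15 = 0.52 points. That study stopped at 25 months and says nothing about Years 3 to 5.

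**The case against.** Four points can be made on the other side.

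- **Scope.** A reader might infer that Section 11.3 flatly contradicts Section 11.2.2 for everyone. It does not. Section 11.2.2 is limited to subjects after definitive treatment discontinuation, so a subject who completed the regimen and has a filler at Year 3 falls outside it. This stands.
- **Inference.** Section 11.3 does not name fillers, and it permits withdrawal without requiring it. Exclusion criterion 15 screens out people who already plan such treatments. A reader might also infer that removal would be selective, by returning folds or by site. That is plausible, but nothing in the documents shows it. The textual route remains open all the same, because Section 8.8 makes the procedure a breach and a change of mind over 5 years cannot be screened out.
- **Not lost from the analysis.** A reader might infer that these subjects drop out of the safety answer. They stay in the ITT denominator with their data up to withdrawal, and Section 12.4 calls for an early termination visit. The SAP adds multiple imputation, the Completer2 and Completer5 analyses, and a listing and sub-classification of discontinuation reasons. This also stands, but all of these analyses are sensitivity analyses. Imputation models later events without observing them, and the candidate covariates visible in SAP Section 5.2.1 are baseline characteristics and number of injection sessions.
- **Size.** A reader might infer a shortfall against 604 or against the darker-skin commitments. The documents do not support that, because such withdrawals may already lie inside the implied 30%. Pivotal onset was also mostly early (median 160 days for nodules, 55 for papules), which limits how many first events a late withdrawal would hide.

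**Conclusion.** The concern holds as a design weakness with a known direction and an unknown size. As written, Section 11.3 allows safety observation to end for noncompliance, the foreseeable noncompliance does not prevent observation, and the formal test then counts the unobserved time as event-free. Any resulting error in the primary incidence is downward.

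The figures of about 0.1 to 1.7 percentage points rest on assumed withdrawal rates, an assumed risk ratio of 1 or 2, an assumed share of late events, and a 25-month pivotal rate used for a 5-year endpoint. They show scale only. With the late-event share suggested by the pivotal study, the result is nearer 0.1 to 0.5 points for 5% withdrawn at equal risk to 10% at doubled risk. This does not show that the primary result is unsound or that the sample size fails. The wording is worth repairing because the repair is cheap and the missed events cannot be recovered afterwards.

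**What to change.** 1. Reconcile Sections 11.2.1, 11.2.2 and 11.3 so that each says whether it ends treatment or follow-up, and for which subjects.
2. In Section 11.3, remove noncompliance, including use of a prohibited product or procedure, as a ground for ending follow-up. Leave other investigator grounds unchanged. Restricting exits to consent withdrawal, death and loss to follow-up would go further than the problem requires.
3. Record such use as a protocol deviation with its date and facial area, and keep the subject in scheduled visits and monthly safety contacts to Year 5.
4. In the SAP, show adverse events of interest before and after that date separately. Let the PP population handle major deviations as already planned, noting that SAP Section 4.3 runs the PP analysis only when PP and ITT differ by at least 5%.
5. Use the sub-classified discontinuation reasons in SAP Section 4.4.5 to report how many subjects were withdrawn by the investigator for noncompliance.
6. Align the synopsis, which says no imputation is made after discontinuation, with Section 13.7, which assumes no events.

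The cost is a short amendment with the FDA and IRB approval that Section 24 requires, plus one added SAP display. Concomitant treatments are already reviewed at each visit, so the extra data are few. The downside is modest: an event arising after another filler in the same area cannot be attributed with certainty to either product. The recorded date and area separate such events in time and place but do not settle their cause.

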11.4 CONSEQUENCE

Subjects who have been withdrawn from the study cannot be reincluded in the study. Their subject number must not be reused. In specific situations to be discussed between Investigator and Sponsor or designee, subjects who have not yet been treated can be reincluded in the study with a new number.

12 STUDY PROCEDURES

12.1 VISIT SCHEDULE

The purpose of the study, benefits, risks, study visit schedule, and the main aspects of the study design will be discussed individually with each subject by the study site personnel. The subject will have the opportunity to ask the Investigator any questions prior to enrolling in the study.

Subjects will be recruited from the outpatient population seeking treatment for contour dermal deformities of the NLF area and other facial areas.

12.1.1 Visit 1 (Day 1) – Screening/initial treatment

The following procedures will be performed during Visit 1 (listed in recommended order):

Protocol GLI.04.SPR.US10321

CONFIDENTIAL

- C
- The subject must sign the informed consent form, initial and date "A Patient's Guide to Treatment with Sculptra® Aesthetic," HIPAA authorization, and photographic consent for the study.
- Assign a unique subject number to the subject. This number will be entered in a CRF used to identify that subject over the course of the clinical trial.
- Review inclusion/exclusion criteria.
- Review the subject's medical history and prior/concomitant medications and treatment procedures.
- Perform physical examination (overall subject assessment and skin assessment, particularly the facial area; height and weight)
- Collect vital signs (sitting heart rate and blood pressure)
- Collect urine and perform a pregnancy test on the specimen (females of childbearing potential only). Results must be negative to continue into the study.
- The clinical Investigator will visually inspect the subject's NLFs and determine severity based on the photo-numeric wrinkle assessment scale (see Appendix II). These will be recorded as the baseline measurements.

NOTE: The subject $\underline{\text{must}}$ have a grade of ≥ 2 and ≤ 4 on the photo-numeric wrinkle assessment scale (see Appendix II) of the left and right $\underline{\text{NLFs}}$ to continue the screening process and be enrolled into the study.

- The clinical Investigator will measure the length of the subject's NLFs. This will be recorded as the baseline measurement.
- Assess Fitzpatrick skin type (see Appendix I)
- The clinical Investigator will visually inspect the subject's other facial wrinkles that are planned to be treated and determine severity based on the Assessment Scale for Other Facial Wrinkles (see Appendix III). These will be recorded as the baseline measurements.
- The clinical Investigator will measure the length of the subject's other facial wrinkles that are planned to be treated. These will be recorded as the baseline measurements.
- If the subject meets all of the study requirements, take photographs of each area that will be treated (see the manual of photographic procedures). Standardized photographs must be taken prior to administration of any injection. This photo will serve as the baseline photograph.
- The clinical Investigator will measure the grid (length and width) corresponding to the area of each wrinkle to be treated.
- Perform initial treatment in accordance with instructions for use (see the Sculptra® Aesthetic package insert). If a local anesthetic is injected, then the WAS must be assessed, after administration of local anesthetic (prior to injection of Sculptra® Aesthetic), and after injection of Sculptra® Aesthetic. A maximum of 10 mL (5 mL per side of the face), 2 vials of Sculptra® Aesthetic, is allowed at each injection session and is up to the discretion of the Investigator.
- Take post-treatment photographs (see the manual of photographic procedures).
- Distribute diary card.

CONFIDENTIAL

- Schedule the subject's next visit in 3 weeks (±3 days).
- Review subject contact information.

12.1.2 Visit 2 (Week 3) – second treatment, if needed

The following procedures will be performed (listed in recommended order):

- All adverse events will be collected including, but not limited to:
 - Adverse events of interest: nodule, papule, hypertrophic scarring, keloid formation, granuloma (confirmed by a biopsy), changes in skin pigmentation, skin necrosis, hypersensitivity reaction, and unexpected changes in wrinkle contour
 - Adverse events reported in more than 1% of subjects during clinical trials regardless of relationship to the device/procedure: injection-site edema, injection-site tenderness, injection-site erythema, injection-site pain, injection-site bleeding, injection-site itching, injection-site bruising, injection-site inflammation, injection-site discomfort, injection-site infection, injection-site acne, injection-site dermatitis, and injection-site skin dryness; nasopharyngitis, headache, hypertension, fracture, urinary tract infection, tooth abscess, syncope, and cough
 - Adverse events reported in less than 1% of subjects during clinical trials regardless of relationship to the device/procedure: sinusitis, influenza, bronchitis, acrochordon, anxiety, colitis, contusion, corneal abrasion, cyst, depression, dermatitis, eczema, gastritis, herpes simplex, hypercholesterolemia, hypersensitivity, hypothyroidism, injection site desquamation, injection-site rash, lower respiratory infection, lymphadenopathy, migraine, muscle injury, muscle twitching, myalgia, osteoarthritis, osteopenia, rheumatoid arthritis, gastroenteritis, skin burning sensation, spider vein, staphylococcal infection, stress symptoms, tooth infection, toothache, and vaginal infection
 - Adverse events reported during postmarketing surveillance regardless of relationship to the device/procedure: allergic reaction, angioedema (Quincke's edema), application site discharge, fatigue, hypersensitivity reaction, hypertrophy of skin, injection-site abscess, injection-site atrophy, injection-site fat atrophy, injection-site granuloma (including ectropion), injection-site induration, lack of effectiveness, malaise, periorbital nodules, photosensitivity reaction, scar and skin discoloration, skin infection, skin rash, skin roughness, skin sarcoidosis, telangiectasias, and urticarial
- Collect and review the diary card. Record relevant medication use that have occurred since the last visit.
- Subject contact information should be reviewed and updated if needed, at each study visit and monthly safety contact.
- Take standardized photographs (see the manual of photographic procedures).
- The clinical Investigator will visually inspect the subject's NLFs and determine severity based on the photo-numeric wrinkle assessment scale (see Appendix II).
- The clinical Investigator will measure the length of the subject's NLFs.

CONFIDENTIAL

- The clinical Investigator will visually inspect the subject's other facial wrinkles and determine severity based on the Assessment Scale for Other Facial Wrinkles (see Appendix III).
- The clinical Investigator will measure the length of the subject's other facial wrinkles that are planned to be treated.
- Based on the WAS, the Investigator will determine if further injections of Sculptra® Aesthetic are needed;

A treatment session to correct WAS 2 to 4 NLF contour deficiencies consists of multiple deep dermal threading or tunneling injection of 0.1 mL to 0.2 mL of Sculptra® Aesthetic in grid pattern to a maximum of 2.5 mL per NLF per session. Sculptra® Aesthetic injections should be stopped when both NLFs and other facial folds have reached a grade of 0 to 1 on the wrinkle assessment scale (see Appendix II and Appendix III). Correction should be limited to no more than 100% of the defect. [If only one wrinkle has reached the target grade of 0 to 1 the other side should continue to be treated until the target grade is achieved (or a maximum of 4 injection sessions and a maximum of 2.5 mL per NLF per session).] A maximum of 10 mL (5 mL per side of the face), 2 vials of Sculptra® Aesthetic, is allowed at each injection session and is up to the discretion of the Investigator.

If the subject DOES NOTrequire further injections:

- Schedule the three (3) month (±2 weeks) follow-up visit from the date of the INITIAL treatment (Note: not 3 months from this visit date).
- Distribute diary card.

If subject DOES require further injections:

- Note: Only NLFs and other facial wrinkles treated at Visit 1 may be treated at this visit.
- The clinical Investigator will measure the grid (length and width) corresponding to the area of each of the wrinkles to be treated.
- Perform additional injections with Sculptra® Aesthetic in accordance with instructions for use. NOTE: Photographs must be taken of each area that is treated **prior** to any injection and **after** administration of Sculptra® Aesthetic (see the manual of photographic procedures), but not between administration of a local anesthetic and Sculptra® Aesthetic. If a local anesthetic is injected, then the WAS must be assessed, after administration of local anesthetic (prior to injection of Sculptra® Aesthetic), and after injection of Sculptra® Aesthetic.
- Distribute diary card.
- Subjects will be scheduled for next visit in three (3) weeks (± 3 days).

